### **8.3 REPORTING OF SERIOUS ADVERSE EVENTS**

Any AE that meets protocol-defined serious criteria or meets the definition of Adverse Event of Special Interest that require expedited reporting must be submitted immediately (within 24 hours of awareness) to OSRO Safety using the CCR SAE report form. Any exceptions to the expedited reporting requirements are found in Section **8.4**.

All SAE reporting must include the elements described in Section **8.1.6**.

SAE reports will be submitted to the Center for Cancer Research (CCR) at: [[contact]](mailto:[contact]) and to the CCR PI and study coordinator. CCR SAE report form and instructions can be found at:

<https://ccrod.cancer.gov/confluence/display/CCRCRO/Forms+and+Instructions>.

Following the assessment of the SAE by OSRO, other supporting documentation of the event may be requested by the OSRO Safety and should be provided as soon as possible.

### **8.4 WAIVER OF EXPEDITED REPORTING TO CCR**

As overall survival which includes death due to disease progression is part of the study objectives, and captured as an endpoint in this study, death due to disease progression will not be reported in expedited manner to the sponsor. However, if there is evidence suggesting a casual relationship between the study drug and the event, report the event in an expedited manner according to Section **8.3**.

### **8.5 SAFETY REPORTING CRITERIA TO THE PHARMACEUTICAL COLLABORATORS**

Reporting will be per the collaborative agreement.

## **8.6 REPORTING PREGNANCY**

All required pregnancy reports/follow-up to OSRO will be submitted to: [[contact]](mailto:[contact]) and to the CCR PI and study coordinator. Forms and instructions can be found here: <https://ccrod.cancer.gov/confluence/display/CCRCRO/Forms+and+Instructions>.

### **8.6.1 Maternal Exposure**

If a patient becomes pregnant during the course of the study, the study treatment should be discontinued immediately, and the pregnancy reported to the Sponsor no later than 24 hours of when the Investigator becomes aware of it. The Investigator should notify the Sponsor no later than 24 hours of when the outcome of the Pregnancy become known,

Pregnancy itself is not regarded as an SAE. However, congenital abnormalities or birth defects and spontaneous miscarriages that meet serious criteria (Section **8.1.2**) should be reported as SAEs.

The outcome of all pregnancies (spontaneous miscarriage, elective termination, ectopic pregnancy, normal birth, or congenital abnormality) should be followed up and documented.

### **8.6.2 Paternal Exposure**

Male patients should refrain from fathering a child or donating sperm during the study and for 125 days after treatment.

Pregnancy of the patient's partner is not considered to be an AE. However, the outcome of all pregnancies (spontaneous miscarriage, elective termination, ectopic pregnancy, normal birth, or congenital abnormality) occurring from the date of the first dose until 125 days after the last dose should, if possible, be followed up and documented.

## **8.7 REGULATORY REPORTING FOR STUDIES CONDUCTED UNDER CCR-SPONSORED IND**

Following notification from the investigator, CCR, the IND sponsor, will report any suspected adverse reaction that is both serious and unexpected in expedited manner to the FDA in accordance to 21 CFR 31.2.32. CCR will report an AE as a suspected adverse reaction only if there is evidence to suggest a causal relationship between the study product and the adverse event. CCR will notify FDA and all participating investigators (i.e., all investigators to whom the sponsor is providing drug under its INDs or under any investigator's IND) in an IND safety report of potential serious risks from clinical trials or any other source, as soon as possible, in accordance to 21 CFR Part 312.32.

All serious events will be reported to the FDA at least annually in a summary format.

## **8.8 SPONSOR PROTOCOL NON-ADHERENCE REPORTING**

Protocol non-adherence is defined as any noncompliance with the clinical trial protocol, GCP, or protocol-specific procedural requirements on the part of the participant, the Investigator, or the study site staff inclusive of site personnel performing procedures or providing services in support of the clinical trial.

It is the responsibility of the study Staff to document any protocol non-adherence identified by the Staff or the site Monitor on the OSRO Site Protocol Non-Adherence Log. The protocol-specific, cumulative non-adherence log should be maintained in the site essential documents file and submitted to OSRO via [[contact]](mailto:[contact]) on the **first business day of each**

**month over the duration of the study.** In addition, any non-adherence to the protocol should be documented in the participant's source records and reported to the local IRB per their guidelines. OSRO required protocol non-adherence reporting is consistent with E6(R2) GCP: Integrated Addendum to ICH E6(R1): 4.5 Compliance with Protocol; 5.18.3 (a), and 5.20 Noncompliance; and ICH E3 16.2.2 Protocol deviations

## 9 CLINICAL MONITORING

Clinical site monitoring is conducted to ensure that the rights of the participants are protected, that the study is implemented per the approved protocol, Good Clinical Practice and standard operating procedures, and that the quality and integrity of study data and data collection methods are maintained. Monitoring for this study will be performed by NCI CCR Office of Sponsor and Regulatory Oversight (OSRO) Monitoring based on OSRO standards, FDA Guidance E6(R2) Good Clinical Practice: Integrated Addendum to ICH E6(R1) March 2018, and applicable regulatory requirements.

Details of clinical site monitoring will be documented in a Clinical Monitoring Plan (CMP) developed by OSRO. CMPs will be protocol-specific, risk-based and tailored to address human subject protections and integrity of the study data. The intensity and frequency of monitoring will be based on several factors, including study type, phase, risk, complexity, expected enrollment rate, and any unique attributes of the study and the site. OSRO Monitoring visits and related activities will be conducted throughout the life cycle of each protocol, with the first activity being before study start to conduct a Site Assessment Visit (SAV) (as warranted), followed by a Site Initiation Visit (SIV), Interim Monitoring Visit(s) (IMVs), and a study Close-Out Visit (COV).

Some monitoring activities may be performed remotely, while others will take place at the study site(s). Monitoring visit reports will describe visit activities, observations, findings of protocol non-adherence and associated action items or follow-up required for resolution of findings. Monitoring reports will be distributed to the study PI, NCI CCR QA, coordinating center (if applicable) and the OSRO regulatory file.

If protocol non-adherence is identified by the Monitor (i.e., any noncompliance with the clinical trial protocol, GCP, or protocol-specific procedural requirements on the part of the participant, the Investigator, or the site Staff) the Monitor will note the observation, review with site Staff and if unresolved, request that the Staff document the non-adherence on the protocol-specific OSRO Site Protocol Non-Adherence Log (see Section 8.8).

## 10 STATISTICAL CONSIDERATIONS

### 10.1 STATISTICAL HYPOTHESIS

#### 10.1.1 Primary Endpoint(s)

The primary endpoint of this trial is to evaluate the activity of bintrafusp alfa (M7824) as determined by objective response rate (ORR) in two metastatic urothelial carcinoma cohorts:

- Cohort 1: Checkpoint inhibitor naïve
  - Cohort 1A: cisplatin ineligible
  - Cohort 1B: refractory post-platinum therapy

- Cohort 2: Checkpoint inhibitor previously treated patients
  - Cohort 2A: previously achieved a CR/PR
  - Cohort 2B: previously had SD/PD

#### 10.1.2 Secondary Endpoint(s)

- To evaluate the activity of bintrafusp alfa (M7824) in urothelial carcinoma patients as determined by progression free survival (PFS) and overall survival (OS).
- To obtain additional data to evaluate the safety of bintrafusp alfa (M7824) in urothelial carcinoma

## 10.2 SAMPLE SIZE DETERMINATION

### 10.2.1 Cohort 1A: Checkpoint inhibitor naïve patients who are cisplatin-ineligible

In this cohort, it would be desirable to demonstrate that the treatment exceeds a 30% response rate. As such, in this cohort, this trial will be conducted using a Simon minimax two-stage phase II trial design (Simon R, Controlled Clinical Trials 10:1-10, 1989) to rule out an unacceptably low PR+CR rate of 15% ( $p_0=0.15$ ) in favor of an improved response rate of 40% ( $p_1=0.40$ ). With  $\alpha=0.10$  (probability of accepting a poor treatment=0.10) and  $\beta = 0.20$  (probability of rejecting a good treatment=0.20), the first stage will enroll 9 evaluable patients, and if 0 to 1 of 9 have a clinical response, then no further patients will be accrued in this trial. If 2 or more of the first 9 patients have a response, then accrual would continue until a total of 16 evaluable patients have been treated. As it may take up to several months to determine if a patient has experienced a response, a temporary pause in the accrual may be necessary to ensure that enrollment to the second stage is warranted. If there are 2 to 4 patients with a response out of 16 patients, this would be an uninterestingly low response rate. If there were 5 or more of 16 (31.3%) who experienced a response, this would be sufficiently interesting to warrant further study in later trials. Under the null hypothesis (15% response rate), the probability of early termination is 60.0%.

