### 10.2.2 Cohort 1B: Checkpoint inhibitor naïve patients who are refractory post-platinum therapy

In this cohort, it would be desirable to demonstrate that the treatment exceeds a 20% response rate. As such, in this cohort, this trial will be conducted using a Simon minimax two-stage phase II trial design (Simon R, Controlled Clinical Trials 10:1-10, 1989) to rule out an unacceptably low PR+CR rate of 10% ( $p_0=0.10$ ) in favor of an improved response rate of 40% ( $p_1=0.40$ ). With  $\alpha=0.10$  (probability of accepting a poor treatment=0.10) and  $\beta = 0.10$  (probability of rejecting a good treatment=0.10), the first stage will enroll 8 evaluable patients, and if 0 of 8 have a clinical response, then no further patients will be accrued in this cohort. If 1 or more of the first 8 patients have a response, then accrual would continue until a total of 15 evaluable patients have been treated. As it may take up to several months to determine if a patient has experienced a response, a temporary pause in the accrual may be necessary to ensure that enrollment to the second stage is warranted. If there are 1 to 3 patients with a response out of 15 patients, this would be an uninterestingly low response rate. If there were 4 or more of 15 (26.7%) who experienced a response, this would be sufficiently interesting to warrant further study in later trials. Under the null hypothesis (10% response rate), the probability of early termination is 43.1%.

**10.2.3 Cohort 2A:** Checkpoint inhibitor refractory patients with Complete Response (CR) or Partial Response (PR) as per RECIST 1.1

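### Do Sections 10.2.1 to 10.2.3 aim for response rates above 30%, 20% and 15% that designs testing 15%, 10% and 5% cannot demonstrate?

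*Combined protocol and SAP*

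**What the plan says.** Each part of Section 10.2 opens with a target figure. For Cohort 1A it reads "it would be desirable to demonstrate that the treatment exceeds a 30% response rate"; for Cohort 1B, "it would be desirable to demonstrate that the treatment exceeds a 20% response rate". Cohort 2A (Section 10.2.3) uses the same sentence with 15%, and Cohort 2B (Section 10.2.4) with 5%.

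The next sentence makes the link: "As such, in this cohort, this trial will be conducted using a Simon minimax two-stage phase II trial design". The hypothesis follows. In 1A the design is "to rule out an unacceptably low PR+CR rate of 15"%, against an alternative of 40%, with alpha 0.10 and beta 0.20. The null rates in 1B, 2A and 2B are 10%, 5% and 5%. The text labels the null explicitly: "Under the null hypothesis (15% response rate), the probability of early termination is 60.0"%.

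The decision rule for 1A is "If there were 5 or more of 16 (31.3%) who experienced a response", and the consequence is that "this would be sufficiently interesting to warrant further study in later trials". For 1B it is "If there were 4 or more of 15 (26.7%) who experienced a response", with the same consequence; 2A needs 3 of 16 and 2B needs 3 of 21.

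Section 10.1.1 states the primary endpoint as evaluating activity through the objective response rate, with no threshold. Section 10.4.2 requires the response fraction in each cohort with two-sided 80% and 95% confidence intervals.

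**The concern.** To demonstrate that a rate exceeds 30% means to rule out 30%, and a test with a null of 15% does not do that. The linking phrase makes it sound as if the design delivers the stated aim. In 1A, 1B and 2A the aim is double, double and triple the null rate. In 2B the aim and the null are both 5%, so the same sentence seems to do a different job there.

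At stake is over-claiming. A report could present 5/16, 4/15 or 3/16 as having met a protocol aim of showing a rate above 30%, 20% or 15%. The concern is sharper for the checkpoint-naive cohorts, because Section 1.2.1 gives response rates for existing PD-1/PD-L1 inhibitors of 23.5-24% in the upfront setting and 15-21% in second line.

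**Working it through.** **Inputs** (Sections 10.2.1 to 10.2.4). Stage 1 has n1 patients and stops at r1 or fewer responses; the cohort fails at r or fewer of n.

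| Cohort | Aim | p0 | p1 | r1/n1 | r/n | Smallest pass |
|---|---|---|---|---|---|---|
| 1A | 30% | 15% | 40% | 1/9 | 4/16 | 5/16 |
| 1B | 20% | 10% | 40% | 0/8 | 3/15 | 4/15 |
| 2A | 15% | 5% | 25% | 0/12 | 2/16 | 3/16 |
| 2B | 5% | 5% | 20% | 0/12 | 2/21 | 3/21 |

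**Step 1: reproduce the plan's figures.** Early stopping under the null is P(X1 ≤ r1). For 1A this is 0.85^9 + 9 × 0.15 × 0.85^8 = 0.2316 + 0.3679 = 0.5995, printed as 60.0%. For 1B it is 0.90^8 = 0.4305, printed as 43.1%. For 2A and 2B it is 0.95^12 = 0.5404, printed as 54.0%. The differences are rounding.

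The probability of passing at true rate p is the sum over x1 > r1 of Bin(x1; n1, p) × P(X2 ≥ r + 1 − x1), where X2 is binomial on n − n1 patients. For 1A at 15%, the terms for x1 = 2, 3, 4, 5 and 6 or more are 0.0192 + 0.0303 + 0.0192 + 0.0050 + 0.0006 = 0.0743.

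| Cohort | Attained alpha | Power at p1 |
|---|---|---|
| 1A | 0.074 | 0.815 |
| 1B | 0.054 | 0.905 |
| 2A | 0.043 | 0.801 |
| 2B | 0.080 | 0.803 |

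All four meet their stated error rates, and a full search confirms that each is the minimax design for its inputs.

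**Step 2: what a minimum pass shows.** The two-sided 80% Clopper-Pearson interval matches a one-sided 0.10 test.

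| Cohort | Smallest pass | Observed rate | 80% interval | Above p0? | Above aim? |
|---|---|---|---|---|---|
| 1A | 5/16 | 31.3% | 16.1-50.4% | yes | no |
| 1B | 4/15 | 26.7% | 12.2-46.4% | yes | no |
| 2A | 3/16 | 18.8% | 7.1-37.1% | yes | no |
| 2B | 3/21 | 14.3% | 5.4-29.1% | yes | yes (aim = p0) |

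The mismatch is real at the cut-off in three cohorts. If the true rate equals the aim, the probability of passing is 0.53 (1A), 0.35 (1B) and 0.44 (2A). These are points on the power curve between p0 and p1, not error rates the plan claims to control.

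**Step 3: is there a consistent reading of the aim?** A pass always gives an observed rate above it: 31.3 > 30, 26.7 > 20, 18.8 > 15 and 14.3 > 5. Read as a floor for the observed rate among passing results, the sentence is true in all four cohorts.

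**Step 4: can the trial ever support the stronger statement?** Yes, with more responses. The 80% lower limit first exceeds the aim at 8/16 in 1A (31.8%), 6/15 in 1B (22.6%) and 5/16 in 2A (16.1%). If the true rate is p1, the probability of reaching those counts is 0.28, 0.60 and 0.37. The intervals already required by Section 10.4.2 show which case applies.

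**Step 5: what would rewording change?** The sample sizes, stage rules, cut-offs, estimates and intervals would all stay the same.

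**The case for a change.** The best case for a change is that the sentence belongs to the primary endpoint, that its verb claims proof, and that the link presents the design as supplying that proof. The figures also look deliberate. In 1A, 1B and 2A the cut-off is the smallest count whose observed rate exceeds the aim, but in 2B it is not: 2/21 (9.5%) already exceeds 5% and is still classed as too low. The sentence is therefore not used in quite the same way throughout.

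The wording is loose, and a minimum pass in three cohorts does not establish the aim. It does not follow that the four sections contradict one another. The 2B discrepancy arises only if the aim must be the tightest floor compatible with the cut-off, and nothing in the plan requires that. A blanket statement that a positive cohort cannot support a rate above the aim would be wrong for the larger passes in Step 4.

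A weightier objection concerns the null rates. In 1A and 1B, p0 lies below the checkpoint-inhibitor rates cited in Section 1.2.1. A drug performing at those rates would pass with probability 0.30-0.32 in 1A (23.5-24%) and 0.17-0.38 in 1B (15-21%), and Section 12.1 stresses the need to improve on about 20%. That is a fair design question, but it concerns the choice of p0. Rewording the aim sentence neither raises nor answers it.

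**Conclusion.** No change follows. The aim sentences in Sections 10.2.1 to 10.2.3 are loosely worded: a minimum pass rules out 15%, 10% or 5%, with 80% lower limits of 16.1%, 12.2% and 7.1%, and does not by itself show a rate above 30%, 20% or 15%. But the sentences express a wish and control nothing. An analyst following the plan would use the stated p0, p1, stage rules and cut-offs, report the required intervals, and conclude no more than that further study is warranted. That conclusion is sound, and it is the same with or without different wording.

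This rests on two assumptions: that the aim figures enter no decision, as the text indicates, and that the report carries the Section 10.4.2 intervals beside any statement about the aims. Whether p0 of 15% in 1A and 10% in 1B is adequate against the cited rates is left open here and should be judged separately.

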### 10.2.2 Cohort 1B: Checkpoint inhibitor naïve patients who are refractory post-platinum therapy

In this cohort, it would be desirable to demonstrate that the treatment exceeds a 20% response rate. As such, in this cohort, this trial will be conducted using a Simon minimax two-stage phase II trial design (Simon R, Controlled Clinical Trials 10:1-10, 1989) to rule out an unacceptably low PR+CR rate of 10% ( $p_0=0.10$ ) in favor of an improved response rate of 40% ( $p_1=0.40$ ). With  $\alpha=0.10$  (probability of accepting a poor treatment=0.10) and  $\beta = 0.10$  (probability of rejecting a good treatment=0.10), the first stage will enroll 8 evaluable patients, and if 0 of 8 have a clinical response, then no further patients will be accrued in this cohort. If 1 or more of the first 8 patients have a response, then accrual would continue until a total of 15 evaluable patients have been treated. As it may take up to several months to determine if a patient has experienced a response, a temporary pause in the accrual may be necessary to ensure that enrollment to the second stage is warranted. If there are 1 to 3 patients with a response out of 15 patients, this would be an uninterestingly low response rate. If there were 4 or more of 15 (26.7%) who experienced a response, this would be sufficiently interesting to warrant further study in later trials. Under the null hypothesis (10% response rate), the probability of early termination is 43.1%.

**10.2.3 Cohort 2A:** Checkpoint inhibitor refractory patients with Complete Response (CR) or Partial Response (PR) as per RECIST 1.1

In this cohort, it would be desirable to demonstrate that the treatment exceeds a 15% response rate. As such, in this cohort, this trial will be conducted using a Simon minimax two-stage phase II trial design (Simon R, *Controlled Clinical Trials* 10:1-10, 1989) to rule out an unacceptably low PR+CR rate of 5% ( $p_0=0.05$ ) in favor of an improved response rate of 25% ( $p_1=0.25$ ). With  $\alpha=0.10$  (probability of accepting a poor treatment=0.10) and  $\beta = 0.20$  (probability of rejecting a good treatment=0.20), the first stage will enroll 12 evaluable patients, and if 0 of the 12 have a clinical response, then no further patients will be accrued in this trial. If 1 or more of the first 12 patients have a response, then accrual would continue until a total of 16 evaluable patients have been treated. As it may take up to several months to determine if a patient has experienced a response, a temporary pause in the accrual may be necessary to ensure that enrollment to the second stage is warranted. If there are 1 to 2 patients with a response out of 16 patients, this would be an uninterestingly low response rate. If there were 3 or more of 16 (18.8%) who experienced a response, this would be sufficiently interesting to warrant further study in later trials. Under the null hypothesis (5% response rate), the probability of early termination is 54.0%.

**10.2.4 Cohort 2B.** Checkpoint inhibitor refractory patients with Stable Disease (SD) or Progressive Disease (PD) as per RECIST 1.1

In this cohort, it would be desirable to demonstrate that the treatment exceeds a 5% response rate. As such, in this cohort, this trial will be conducted using a Simon minimax two-stage phase II trial design (Simon R, *Controlled Clinical Trials* 10:1-10, 1989) to rule out an unacceptably low PR+CR rate of 5% ( $p_0=0.05$ ) in favor of an improved response rate of 20% ( $p_1=0.20$ ). With  $\alpha=0.10$  (probability of accepting a poor treatment=0.10) and  $\beta = 0.20$  (probability of rejecting a good treatment=0.20), the first stage will enroll 12 evaluable patients, and if 0 of the 12 have a clinical response, then no further patients will be accrued in this trial. If 1 or more of the first 12 patients have a response, then accrual would continue until a total of 21 evaluable patients have been treated. As it may take up to several months to determine if a patient has experienced a response, a temporary pause in the accrual may be necessary to ensure that enrollment to the second stage is warranted. If there are 1 to 2 patients with a response out of 21 patients, this would be an uninterestingly low response rate. If there were 3 or more of 21 (14.3%) who experienced a response, this would be sufficiently interesting to warrant further study in later trials. Under the null hypothesis (5% response rate), the probability of early termination is 54.0%.

These phase II cohorts treated with TGFB trap alone may require up to  $15+16+16+21=68$  evaluable patients. To allow for a small number of inevaluable patients, this trial of up to 4 different cohorts will have an accrual ceiling of 75 patients. It is expected that 2-3 patients per month may enroll onto the trial; thus, it is expected that this trial may complete accrual in 2 to 3 years.

**10.3 POPULATIONS FOR ANALYSES**

Modified intention to treat: all patients who receive at least one dose of each agent will be included in the statistical analyses performed.

## **10.4 STATISTICAL ANALYSES**

### 10.4.1 General Approach

Response fractions, and time to event endpoints will be reported along with appropriate confidence intervals.

### 10.4.2 Analysis of the Primary Endpoints

Separately by cohort, the fraction of patients in phase II cohorts who experience a PR or CR using the study treatment will be determined by dividing the number responders by the total evaluable patients. The fraction will be reported along with 80% and 95% two-sided confidence intervals.

